#### VISIT 2 (MRI VISIT)

Overall Plan: UCD Research MRI (Brain Imaging Center): Participants will be asked to fast for 4-6 hours prior to this visit. The imaging will be of the liver. Two different studies may be conducted. One will be standard MRI of the mid abdomen to assess the amount of subcutaneous fat, visceral fat and percent liver fat. The second type of scan is optional pending scheduling. It will be P spectroscopy to measure the concentrations of phosphate molecules including PDE, PME and PCr. Vascular Endothelial function

and Heart Rate Variability will be assessed with Endopat and Dynapulse, which take approximately 30 minutes.

#### P MRS of the Liver and Abdominal Imaging (pending scheduling)

MRS Data acquisition: Imaging and MRS will be performed on a Seimens 3 Tesla MRI magnet. A custom H/P abdominal coil will be used for imaging and MRS (Clinical MR Solutions, Brookfield, WI) as in our previous P work. The coil will be a concentric probe with an inner coil 16 cm in diameter (for P) and a 20 cm outer coil (for H scout imaging and shimming). A 2 cm x 2 cm x 2 cm area of focus is found in the liver in homogenous tissue for MRS, similar to our previous studies. A P MRS scan will then be performed for baseline measurements. We will continue to work with our current collaborators [name], Assistant Professor, Department of Radiology, UC Denver Anschutz and [name], Professor, Department of Radiography, University of Alabama at Birmingham to optimize the MR signal collection. Visceral adiposity will be measured using the gold standard of an MRI slice at L4-L5. Hepatic fat fraction will be performed using modification of the Dixon method as in our previous studies. Hepatic fibrosis will be measured with a fibroscan sequence.

MRS Data Analysis: For the P data, peak positions and areas of interest [phosphocreatine (PCr), inorganic free phosphate (Pi), β-ATP(3 peaks), α-ATP(2 peaks), γ-ATP(2 peaks), and PME] will be determined by time domain fitting with jMRUI, utilizing AMARES (A Method of Accurate, Robust and Efficient Spectral fitting), a nonlinear least-square-fitting algorithm using our previously built prior knowledge files. We have utilized this method for muscle P analysis for the previous 6 years, and have extensive experience with this analysis. The adipose data will be analyzed by radiology MRI research imaging, supervised by [name], as in previous protocols (COMIRB #'s 10-1288 and 14-0542).

Gut Bacteria Collection: The gut microbiome consists of the microorganisms, predominantly bacteria, that inhabit the gastrointestinal tract and are estimated to outnumber mammalian cells by up to a factor of 10, and their genes outnumber human genes by a factor of over 100 [69]. It is possible that gut microbiota contribute to the development of NAFLD, and this has not been explored in PCOS. We will collect a sample to define the microbiota in girls who are already undergoing extensive metabolic profiling. The gut microbiota will be collected with BBL culture swabs (Becton, Dickinson and Company, Sparks, Maryland) one week prior to visit 3. Fecal samples will be collected from the first bowel movement of any day the week before visit 3 and stored in the freezer. Fecal samples are being collected for present and future research markers in the microbiome. Fecal samples are routinely collected in research and pose little risk to participants. For all samples, bacterial DNA will be extracted from the swab using established methods and the V4 region of 16S bacterial rRNA will be amplified using previously published primers and PCR conditions. [66, 67, 68] To provide a full picture of microbial diversity in the gut, we have combined phylogenetic and Operation Taxonomic Units (OTC)-based methods for comparing communities. Grouping bacterial rRNA sequences by similarity is important for asking questions about which particular species, genera, phyla, etc, contribute to differences between samples. To choose OTUs, groups of similar 16S bacterial rRNA sequences are identified, and candidate OTUs are identified as sets of sequences connected to each other. Candidate OTUs are considered valid if the average density of connection is above 70% (i.e., if 70% of the possible pairwise connections between sequences in the set exist).

Accelerometer: One week prior to the overnight visit, the participant will be provided two accelerometers (GT3X BT by Actigraph and ActiWatch by Philips Respironics) to be worn for seven days to measure level of habitual physical activity, which affects insulin sensitivity, and sleep patterns. Accelerometers are effective tools for the objective measurement of physical activity because they have the ability to continuously record physical activity data and such data can be used to estimate METs of activity. They provide more detailed information than pedometers, which only measure walking steps, and help get around the recall bias of questionnaires. We are currently using the GT3X BT Actigraph in adolescents in our other diabetes studies; therefore, we are familiar with their use in this population and have the necessary computer software and interpretation skills. The Actiwatch is being used as a tool for objective measurement of sleep patterns. The Actiwatch is fitted with a LED monitor that detects multiple spectrums of light to better assess sleep patterns in this population.

**\*One week prior to overnight visit, participant will receive via mail the accelerometers, sleep diary and stool sample collection kit (Gut bacteria collection) \***

### **VISIT 3 (ORAL GLYCEROL TRACER WITH D2O AND ORAL SUGAR TOLERANCE TEST)**

Children's Hospital Colorado or University Hospital CTRC Inpatient unit Only under extenuating circumstances, if no rooms available in either hospital, we may have patients go home after WatchPAT is placed, and drink deuterated water at home, and come back the following morning at 6am: Participants will be asked not to have caffeine or exercise for 3 days prior to this visit. During admission, participant will be provided with a study diet dinner and snack. Patients will be admitted to the Pediatric CTRC for a monitored overnight fast. Participants will be questioned regarding changes in concomitant medications and medical history, height, weight, BP. Participants will also have a Fibroscan (liver ultrasound) on the day of admission or the morning of the OSTT (pending staff availability).

A DEXA scan will be performed to assess body composition. A urine pregnancy test will be done on all female participants prior to the DEXA scan. If a female participant is confirmed to be pregnant, she will be withdrawn from the study and referred to her primary care physician for follow-up.

The following morning, a blood sample for baseline metabolic labs will be drawn the modified OSTT will be completed (**Figure 10**). Additional blood will be drawn and stored for future inflammatory markers as well as for targeted and untargeted metabolomics analysis.

WatchPAT: During the hospital overnight stay, trained study staff will place the WatchPAT sleep monitor. The primary measures will be for oxygen saturation and apnea hypopnea index (AHI). Each participant will wear the watch with a one-time use finger cuff as recommended by the FDA. The watch will be placed by 8 PM, and will be removed the following morning. The watch pat data collection will not be ideal, due to waking the participants to drink the deuterated water. However, the primary endpoint is the apnea hypopnea index, and we can still get a rough estimate of this information, even with less than ideal sleep.

Details of Stable Glycerol Isotope Tracer studies with an OSTT: Participants will fast overnight, and drink 3 doses of D2O three times during the night with doses at 6-8PM, 10-11 PM and 2-3 AM as described previously in obese youth. The total D2O to be given (3 mL per kg of body water) is designed to raise body deuterium levels to 0.3% and was administered in three doses to maintain the steady state until the end of the study. Serum samples will be collected in the morning before the glycerol, and then throughout the OSTT, and VLDL TG separated and then enrichment in palmitate measured. By evaluating the incorporation of the D2O into palmitate, we will be able to assess the DNL expressed as a percentage of DNL. We will also measure the rate of gluconeogenesis by measuring the enrichment in serial plasma glucose samples.

The following morning at approximately 7:00AM, a 50 mg/kg of an oral C-glycerol tracer will be consumed mixed with water. Blood samples will be collected and at approximately 10AM, participants will consume a 75 gram glucose load with an additional 25 grams of fructose to stimulate hepatic de novo lipogenesis. Analysis of serum glucose isotopomers will be performed by our collaborator [name] at UT Southwestern, using NMR isotopomer analysis and pathway modeling software. Lipolysis will be modeled using FFA concentrations and whole body IR by a time modified version of the Matsuda model.

Using a metabolic cart and hood, resting VO2 (ml/kg/min) and VCO2 (ml/kg/min) measurements (REE) will be collected the morning of the OSTT prior to the start of the OSTT, and two more times during the OSTT. This is required to determine what portion of ingested carbohydrates are subject to oxidative and non-oxidative glucose disposal.

Study diet: Variations in diet, activity and circadian rhythms affect metabolism^121. Therefore, OSTT studies will be performed in the AM, in the follicular phase where possible, preceded by 3 days of no strenuous physical activity. Participants will be advised to eat a typical diet for the 3 days preceding the study. On the day of study, they will have a snack and dinner selected from limited choices on the Children's hospital carbohydrate counting diet plan, with at least 20 grams of carbs in the snack and 40 grams of carbs for dinner. Participants will ingest their study drink (amino acid or placebo) in the morning of the day of admission, and then after the MRI with their snack.

**Note:** Participants will stop taking placebo or EAA supplements after completion of overnight visit for approximately 4 weeks (washout period). Then participants will crossover to EAA or placebo. The pharmacy will dispense the proper supplement, since study staff and participant will be blinded. The participant will be scheduled for Visits 4 and 5 after being on placebo or EAA supplements for 4 weeks.

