#### Inclusion Criteria:

- 1) Female
- 2) Ages 12-21
- 3) Sedentary- less than 2 hours of moderate (jogging, swimming etc) exercise a week.
- 4) BMI equal or greater than the 90th percentile for age and gender

5) PCOS per the most stringent NIH criteria adapted for adolescents (irregular menses >24 months post-menarche and clinical or biochemical hypertestosteronemia)

6) HS per FibroScan ultrasound, with CAP score of >225.

[figure not shown]

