#### Exclusion Criteria:

1. Use of medications known to affect insulin sensitivity: metformin, oral glucocorticoids within 10 days, atypical antipsychotics, immunosuppressant agents, HIV medications, hormonal contraception. Dermal patch or vaginal ring contraception methods.
2. Currently pregnant or breastfeeding women. Development of pregnancy during the study period will necessitate withdrawal from the study.
3. Severe illness requiring hospitalization within 60 days
4. Diabetes, defined as Hemoglobin A1C > 6.4%
5. BMI percentile less than the 90th percentile for age and sex. Weight >325 lbs or <84 lbs.
6. Anemia, defined as Hemoglobin < 11 mg/dL
7. Diagnosed major psychiatric or developmental disorder limiting informed consent
8. Implanted metal devices that are not compatible with MRI
9. Use of blood pressure medications
10. Known liver disease other than NAFLD or AST or ALT >125 IU/L

[figure not shown]

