samples are collected at frequent intervals per **Figure 10** for positional NMR isotopomer analysis by collaborator [name] at UT Southwestern. Analyses will include modeling metabolic flux utilizing custom designed software and endpoints will include rates of excess TCA cycling contributing to triglyceride synthesis and gluconeogenesis as shown in **Figure 8**. This will be followed by a OSTT (75-gram glucose and 25-gram fructose) with frequent sampling of glucose, insulin, C-peptide. Fasting insulin sensitivity will be calculated with HOMA-IR (fasting glucose\* fasting insulin/22.4). The Matsuda index will be used to estimate whole body post-prandial insulin sensitivity and indices of hepatic [Glucose0–30(AUC)/insulin0–30(AUC)] and muscle insulin sensitivity [dGlucose/dtime ÷ insulin] with calculations starting at the downslope of glucose concentration. Blood glucose will be measured at the 2 hour time point and >140 mg/dL is defined as impaired glucose tolerance. Rates of fasting gluconeogenesis will be measured from the tracer incorporation of deuterated water into glucose, with samples analyzed with GCMS by collaborator [name], as previously described in youth. **Metabolomics:** Targeted amino acid and amino acid breakdown product metabolomics profiles will be measured by the University of Colorado metabolomics core on fasting and 120 minute post glucose drink samples (<https://www.dalessandrolab.com/home>).

Study Calendar	Screen	Phase I		Phase 2	
	Visit 1	Visit 2 –MRI	Visit 3 – Overnight	Visit 4 –MRI	Visit 5 – Overnight
Consenting and Eligibility Assessment	X				
History & Physical	X				
Intravenous Blood Draw	X		X		X
Fibroscan -Liver ultrasound	X		X		X
Randomization- Placebo vs EAA	X				
Crossover- Placebo vs EAA			X		
Accelerometer teaching	X				
Gut Bacteria Collection			X		X
Urine Pregnancy Test			X		X
Questionnaires- SEARCH Food frequency, Activity 3DPA, Strengths and Difficulties and Sleep assessments			X		X
DEXA Scan (located in Leprino building)			X		X
Oral Glycerol Tracer with D 2 O			X		X
Oral Sugar Tolerance Test (OSTT)			X		X
WatchPAT sleep study			X		X
Metabolic Cart			X		X
EndoPat and Dynapulse		X		X	
MRI of abdomen and liver		X		X	
P MRS of Liver		X		X	
Total Time of visit (approximately)	2 Hours	2 Hours	22 Hours	2 Hours	22 Hours

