### Overall enrollment procedure plan per group

#### VISIT 1 (SCREEN VISIT)

Pediatric CTRC Outpatient unit: Participants will begin with a medical screening and physical exam for inclusion/exclusion criteria evaluation. During this visit, patients will review and complete consent documents, have demographics and medical history confirmed, assess allergies and further evaluation of inclusion/exclusion criteria, have blood samples drawn, and have anthropometrics completed. HbA1c, ALT, AST, CBC panel and testosterone panel will be drawn at the beginning of the visit after consent in all participants. PCOS labs may be performed for confirmation of PCOS status, if not performed previously. Whole blood for DNA samples for future genetic analysis associated with hepatic steatosis will also be drawn and stored at this time. Participants will also have a Fibroscan (liver ultrasound) to check for HS (CAP score of >225).

After eligibility assessment, participants who qualify for the study will be randomized to placebo or EAA by the pharmacy. Both study staff and participant will be blinded. The participant will be scheduled for Visits 2 and 3 after being on placebo or EAA supplements for 4 weeks.

Screening lab test	Purpose for test
HbA1C	Rule out type 2 diabetes, if > 6.4% participant to be excluded
ALT, AST	Ensure no severe liver disease, if >125 IU/L participant to be excluded normal participant is excluded
Hemoglobin & Hematocrit (part of CBC)	If participant is Anemic, they will be excluded
Testosterone	Test for hyperandrogenism – required to meet NIH criteria for PCOS
Optional PCOS labs	
PCOS status must be confirmed prior to enrollment. Referring physicians often do not perform the entire recommend work-up for oligomenorrhea (per 2013 Endocrine Society Clinical Guidelines for PCOS). The values are typically expected in PCOS publications	
TSH, total T4	Ensure no hypo or hyperthyroidism causing amenorrhea
LH, FSH	Rule out primary ovarian failure
17-hydroxyprogesterone	Rule out late onset congenital adrenal hyperplasia
DHEAS	Rule out adrenal tumor
Prolactin	Rule out prolactin secreting brain tumor

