### **1. Blood Sampling**

**Description:** Blood will be drawn for Complete Blood Count (CBC), HbA1c, total and free testosterone, and sex hormone binding globulin. If participants have not had a full evaluation for oligomenorrhea, Prolactin, DHEAS, LH, FSH, TSH, total T4 or 17-OH progesterone may be drawn.

**Risk:** Minimal. Risk of pain, bruising at site of blood draw, excessive amount of blood.

**Minimizing Risk:** Certain studies at our institution draw over 7ml/kg in 6 weeks, or up to 7 ml/kg in a single draw, but include iron supplementation. Otherwise, the routine guidelines in our Pediatric CTRC are 2.5ml/kg for a single draw and no more than 5 ml/kg over a 4 week period. Our baseline visit will include 11.5 ml of blood (HbA1c, Hb, Cr, AST, ALT) and 25.5 ml of blood for PCOS patients (additional draw for T4, TSH, prolactin, LH, FSH, 17OH progesterone and DHEAS). The OSTT visit includes up to 300 ml of blood which will occur within 4 weeks of the initial visit. Thus, our OSTT visit is within the NIH Clinical Center guidelines of 9 ml/kg in 6-8 weeks and within Children's Hospital Colorado's institutional guidelines of 5 ml/kg. In addition, by study design, participants are screened by our baseline CBC and excluded if anemic, further increasing the safety of the study regarding blood draws. We will use a minimum weight cutoff of 38 kg to remain below the most conservative pediatric CTRC blood drawing guidelines. This screening also helps to increase the safety of the blood draw. In addition, the blood planned to be frozen and held could also be omitted if needed to reduce blood volume for a particular participant. Finally, our CTRC has a system to track other studies participants might enroll in, and we ask

during our consent process if the participant has been involved in any other studies in the past 6 weeks to avoid excessive blood drawing.

*Justification:* Screening laboratory measurements are necessary to assure that patients meet inclusion/exclusion criteria before any further study is completed. A CBC is necessary as a screening lab, to rule out anemia. A hemoglobin A1c can be used to rule out diabetes. Hormone levels of free and total testosterone, and sex hormone binding globulin are needed to categorize patients as having PCOS, and prolactin, DHEAS, LH, FSH, TSH, total T4 or 17-OH progesterone to rule out other causes of oligomenorrhea, if not done previously.

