## 8. Body Composition

*Description:* Body composition will be measured using the DEXA technique and will be used to derive fat-free mass and % body fat. This technique relies on the absorption of dual electron wavelengths for the assessment of body fat, lean tissue, and bone mineral density. During the procedure, the participant will be supine on the measurement table, and the arm of the machine will slowly pass over their body.

*Risk:* Minimal. Radiation exposure

*Justification/Minimization:* Body composition is best assessed via DEXA, and the amount of muscle mass is needed to standardize the OSTT results, since body weight can vary greatly. This procedure will deliver the radiation exposure that is 2 times the level of background radiation in Colorado. Participants will be tested for pregnancy immediately prior to DEXA, to ensure that they are not pregnant.

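### Pregnancy is an exclusion criterion, but no pregnancy test is listed before randomisation; the first comes about 4 weeks into study product

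*Combined protocol and SAP*

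**What the plan says.** Exclusion criterion 2 in section III.B is "Currently pregnant or breastfeeding women", and the same item requires withdrawal if pregnancy develops during the study. Section VI.C repeats the withdrawal rule.

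The Visit 1 text in section III.C describes the blood tests: "HbA1c, ALT, AST, CBC panel and testosterone panel will be drawn at the beginning of the visit after consent in all participants". It adds optional PCOS labs, a DNA sample and a FibroScan. Randomisation then follows: "After eligibility assessment, participants who qualify for the study will be randomized to placebo or EAA by the pharmacy". The Study Calendar also marks randomisation in the Screen column.

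The calendar row "Urine Pregnancy Test" is marked at Visits 3 and 5 only. The Visit 3 text gives the reason for the timing: "A urine pregnancy test will be done on all female participants prior to the DEXA scan". Section III.D.8 (Body Composition) ties the test to the scan in the same way: "Participants will be tested for pregnancy immediately prior to DEXA, to ensure that they are not pregnant". Visit 5 refers back to the Visit 3 description. Visits 2 and 3 are scheduled after 4 weeks on EAA or placebo.

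**The concern.** The protocol means to keep pregnant girls out at entry, but its only objective check comes at the end of the first treatment period. At Visit 1 the exclusion rests on history and the general eligibility review. These can pick up a known pregnancy but are poor at finding an unrecognised one in this population. The entry criteria require "irregular menses >24 months post-menarche", so a missed period tells the investigator little, and hormonal contraception is itself an exclusion.

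What is at stake is participant protection and correct eligibility in girls and young women aged 12 to 21. A pregnancy present at entry would become a withdrawal after randomisation when it should have been a screen failure, and referral to the primary care physician would come about a month late.

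**Working it through.** The plan states no figure on this point, so the check sets its sections side by side and then works out the timing.

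**1. Where a Visit 1 pregnancy test could appear**

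| Place | Visit 1 content | Pregnancy test? |
|---|---|---|
| III.C Study Calendar, Screen column | Consent, history and physical, blood draw, FibroScan, randomisation, accelerometer teaching | No |
| III.C Visit 1 text | HbA1c, ALT, AST, CBC, testosterone panel, optional PCOS labs, DNA sample, FibroScan | No |
| III.C screening lab table | HbA1c, ALT/AST, hemoglobin and hematocrit, testosterone; optional TSH, T4, LH, FSH, 17-hydroxyprogesterone, DHEAS, prolactin | No |
| III.D.1 Blood Sampling | CBC, HbA1c, testosterone, SHBG, optional PCOS labs; Cr, AST and ALT also appear in the blood-volume list | No |

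The four places agree, so this is neither a slip in one table nor an artefact of text extraction.

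**2. How other exclusions are verified at screening**

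| Exclusion criterion | Visit 1 test |
|---|---|
| 4, diabetes | HbA1c |
| 6, anemia | Hemoglobin |
| 10, raised transaminases | ALT, AST |
| 2, pregnancy | None listed |

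The optional labs look for thyroid, ovarian, adrenal and prolactin causes of absent or irregular menses. Pregnancy is not among the causes tested.

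**3. Timing**

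Inputs: 4 weeks per treatment period and about 4 weeks of washout (III.C, Overall Study Design).

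- Week 0: randomisation, first product; no test listed.
- Visit 3: about week 4; first listed test.
- Start of second product: 4 + 4 = about week 8; no test listed.
- Visit 5: 4 + 4 + 4 = about week 12; second listed test.
- Gap between the two tests: 12 − 4 = 8 weeks.

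**4. Product taken before the first test**

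Input: 10 g of EAA twice daily (III.C, EAA Supplement).

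- Days: 4 × 7 = 28.
- Doses: 2 × 28 = 56.
- EAA, if it is the first-period product and every dose is taken: 56 × 10 g = 560 g.

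A girl assigned placebo first would take 56 placebo doses and no EAA in that time.

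**5. Effect on the analysis**

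A girl withdrawn at Visit 3 has no second-period liver fat value, so she contributes no pair to the paired t-test or signed rank test in section VII. Section III.B allows enrolment beyond 20 to replace dropouts. The statistical cost is one randomised place to refill, with no loss of power.

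**The case against.** The strongest reply is that little is left once the limits are stated. The product is an amino acid supplement, and the documents show no fetal harm from it. The MRI is described as non-radiation, and the one procedure with radiation, DEXA, is already preceded by a urine test. A positive result leads to withdrawal and referral. The paired analysis cannot be contaminated, because a girl withdrawn at Visit 3 never forms a pair. No pregnancy rate is given, so the size of the gap is unknown. The 560 g figure depends on EAA coming first and on full adherence, and with no dose-related harm claimed it describes duration more than risk.

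All of that stands. It is why this is an eligibility and protection gap and not a threat to the trial's result.

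A second reply concerns the statement in III.D.1 that "Screening laboratory measurements are necessary to assure that patients meet inclusion/exclusion criteria before any further study is completed". It sits in the blood-sampling section and goes on to name anemia, diabetes, androgens and other causes of oligomenorrhea. It does not promise a laboratory test for every criterion. Breastfeeding, medications, recent hospitalisation and implanted metal are all checked without one. This is also fair, so the finding does not rest on that sentence. Those items can be established by asking or from records. An unrecognised pregnancy cannot, and the usual prompt of a missed period is unreliable in this population.

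A third reply is that a Visit 1 test would miss conception during period 1 or the washout. That is true. The Visit 3 test covers conception in period 1 once it is detectable, but a pregnancy starting in the washout would not be tested for until Visit 5. The Visit 1 test still closes the gap at the point where the protocol says pregnant girls are to be excluded.

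**Conclusion.** The concern holds. Followed as written, the plan allows a girl with an unrecognised pregnancy to be randomised against exclusion criterion 2 and to take product for about 28 days before the first listed test. It should be corrected because the change is simple and the participants are aged 12 to 21. It does not alter any endpoint, sample size or analysis.

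The conclusion assumes that the listed procedures are complete. Staff may test at Visit 1 under local practice, but the protocol does not say so. The number of girls affected cannot be estimated from the documents.

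**What to change.** Add the study's existing urine pregnancy test to Visit 1, after consent and before randomisation. Mark it in the Screen column of the Study Calendar and in the screening lab table. Treat a positive result as a screen failure, with the same referral to primary care as at Visit 3. Keep the tests before DEXA at Visits 3 and 5.

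A repeat test before the second product is optional. The calendar has no visit at that point, so it would need a mailed home kit or a check at dispensing.

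The cost is a protocol and calendar amendment and one dipstick per girl at a visit that is already in clinic. That is up to 50 tests if every screened girl is tested. If only girls who pass the FibroScan criterion are tested, it is about 50 × 50% = 25. The 50% is the plan's own screening assumption for hepatic steatosis; the documents give no separate prevalence for a CAP score above 225.
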